3.4 Secondary endpoints/outcomes

- Number of MPX patients attending as a percentage of total number of patients the sites have seen over a set period of time (from first Mpoxy patient to last Mpoxy patient**)
- Length of stay in hospital*** for inpatients treated for MPX.
- Time to lesion resolution (if known)
- Differences in the clinical manifestation of MPX in PLWHIV and PrEP users by co-morbidities.

*Hospitalisations for clinical reasons only (i.e. not for precautionary measures or quarantine).

** This is regardless of if these first and last patients were included in the collected data

***in case of multiple hospitalisations, this will be the sum of the length of all stays.

4 STUDY DESIGN

This is an observational retrospective cohort study.

In total, approximately 2000 cases from PLHIV and PrEP users will be analysed

Only real-world retrospective, routine data will be used for this study. Deidentified data will be transcribed into the Electronic Case Report Form (eCRF) system from source data at each clinical site or from existing cohort databases, where appropriate.

Case data will be collected until the Date of clinical resolution e.g. lesion resolution, hospital discharge or death (up to 3 months)

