Full study Title:	Morbidity, Mortality And Risk Factors of Mpox in HIV negative high-risk Sexual health clinic attenders and People Living With HIV - MASH Study	
Short title/Acronym	MASH	
Clinical Phase	Observational Retrospective Cohort Study	
Study Design	Case-descriptive study	
Study Population	PLWHIV (people living with HIV) who are currently sexually active and HIV negative high-risk Sexual Health Clinic attenders (PrEP users) with Mpox	
End of study data collection	Date of clinical resolution e.g. lesion resolution, hospital discharge or death (up to 3 months)	
Planned Sample Size	Approximately 2000	
Eligibility Criteria	at least 18 years of age with either documented HIV-1 infection or PrEP clinic attenders, and confirmed MPX infection by documented result on PCR testing on skin and/or mucosal and/or any anatomical site.	
Indications	HIV & MPX; PrEP patients & MPX	
Methodology	Only real-world, routinely collected, retrospective data will be used for this study collected from patients who during the study period have had confirmed Mpox. Pseudonymised data will be transcribed into the eCRF (electronic Case Report Form) system from source data at each clinical site or from existing databases, where appropriate. No personal identifiable data will be transmitted to NEAT ID.	
Number of sites	Up to 12 sites in up to 7 countries	
Objectives	
Primary
 
 1. To describe and compare outcomes of MPX in PLWHIV and an HIV-negative population of people using pre-exposure HIV prophylaxis (PrEP users) 2. To identify risk factors for specific MPX outcomes (including CD4 cell count nadir and current CD4 count in PLWHIV) 	
Secondary
 
 1. To estimate the approximate prevalence of MPX in PLWHIV and PrEP users in this retrospective cohort 2. To describe clinical manifestation of MPX and response to MPX treatment in PLWHIV and PrEP users 3. To describe the co-morbidities in PLWHIV and PrEP users

Outcome Measures	Primary	Secondary

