6.2 Data collection

Only real-world retrospective data will be used for this study. Patients who have had mpox and fulfil the entry criteria will be enrolled after 90 days from date of diagnosis to allow for follow up data to be collected. Pseudonymised retrospective data will be transcribed into the eCRF system from source data at each clinical site or from existing cohort databases, where appropriate. No personal identifiable data will be transmitted to NEAT ID. The data elements will be transcribed from source data according to the data collection list below. Mechanisms to ensure data quality and integrity will be deployed as per applicable standard operating procedures and in line with Good Documentation Practice (GDocP) and Good Pharmacoepidemiology Practice (GPP). Patients will be identified and documented by participating sites.

For all patients with MPX the following information will be collected where routinely available:

- Age (year of birth)
- Sex and gender identity
- Ethnicity (where available)
- HIV status
- HIV pre-exposure prophylaxis (PrEP) use
- Comorbidities and Medical history (diabetes mellitus, other immunosuppression (e.g. solid organ transplant), known chronic kidney or liver disease, mental health conditions)
- Recent sexual history (3 months) – number of recent partners
- Recent and/or concomitant sexually transmitted infections
- Orthopoxvirus vaccination history (if available)
- Symptom onset date (fever onset, lesion onset, rectal pain)

- Date of positive PCR test result (documented)
- MPX severity -Reported clinical signs and symptoms of mpox (e.g. rash, mouth lesions, rectal pain, breathlessness)
- Time to resolution of lesions, if known
- Mortality as a consequence of MPX including cause
- Hospitalisation for MPX and length of hospitalisation
- Drug treatment for MPX (Tecovirimat, other)
- Drug for complications associated with MPX (laxatives, antibiotics, analgesia)
- recent travel to/living in endemic country or country with outbreak
- contact with suspected, probable, or confirmed case (if known)
- contact with infected animal (if known)

For PLWHIV the following additional information will be collected:

- Date of HIV diagnosis
- Current Antiretroviral Therapy/Treatment (ART)
- If not on ART, reason for not being on ART
- Last CD4 cell count (including CD4% and CD4/CD8 ratio) and
- Last HIV-RNA before MPX diagnosis

Skin lesion at peak severity score:

- Not presenting with skin lesions (0 skin lesions)

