7.4 Primary outcome analysis

The first primary outcome analysis will be to describe outcomes of MPX in PLWHIV and in PrEP users in terms of severity of lesions, time to lesion resolution, hospitalization, death.

The rate of serious lesions will be estimated by dividing the number of participants with serious lesions by the total number of participants in the full analysis population. Unadjusted and adjusted odds ratios (ORs) will be calculated using the logistic regression model to assess the impact of HIV on the occurrence of serious lesions compared to PrEP users.

Because some participants' lesion may not be healed by the end of the study period and, therefore, the duration of resolution would not be known, and thus right-censored, survival analysis methods such as the Kaplan-Meier and Cox model will be used to assess the time to lesion resolution. Kaplan-Meier estimates will be used to estimate the median time to lesion resolution. Unadjusted and adjusted hazard ratios (HR) will be estimated using the Cox proportional hazard model to assess the impact of HIV-infection on the time to lesion resolution compared with PrEP users.

The hospitalization rate will be estimated by dividing the number of participants hospitalized for mpox infection by the total number of participants in the total analysis population. Unadjusted and adjusted odds ratios (ORs) will be calculated using the logistic regression model to compare hospitalization rates between PLWHIV and PrEP users.

The mortality rate will be estimated using the Kaplan-Meier Method. Unadjusted and adjusted hazard ratios (HR) will be calculated using the Cox proportional hazard model to compare the rates of mortality between PLWHIV and PrEP users.

Adjustment variables will include the following potential confounders: Age (<30 vs 30-40 vs >40 years); Sex at birth (female vs male); Comorbidities; multiple sexual partners (yes vs no); number of sexual partners in the last 3 months prior to mpox diagnosis; and smallpox vaccination history (yes vs no).

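### The end-of-data rule counts hospital discharge as clinical resolution with no order of precedence, so inpatients' follow-up for lesion healing may close early or be misrecorded

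*Combined protocol and SAP*

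**What the plan says.** The synopsis and section 4 define when a case closes. Section 4 reads "Case data will be collected until the Date of clinical resolution e.g. lesion resolution, hospital discharge or death (up to 3 months"). Appendix 2 records that this end point was added in version 3.0. The three dates are examples joined by "or"-type wording, with neither a first-to-occur nor a last-to-occur rule. No other section says when a case closes.

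Four other places bear on it:

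- Section 6.2: patients "will be enrolled after 90 days from date of diagnosis to allow for follow up data to be collected".
- Section 6.2, items for all patients: "Time to resolution of lesions, if known".
- Section 3.4, footnote on length of stay: "in case of multiple hospitalisations, this will be the sum of the length of all stays".
- Section 7.4: "survival analysis methods such as the Kaplan-Meier and Cox model will be used to assess the time to lesion resolution". The only reason given for censoring is that lesions "may not be healed by the end of the study period"; discharge is not mentioned.

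Section 7.5 uses discharge only to end the hospital stay.

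**The concern.** Discharge is not healing. The admission reasons listed in sections 1 and 2 include pain control, superinfection and poor oral intake, and these can settle while lesions remain. Section 1 puts the usual illness at 2 to 4 weeks, and section 2 says that some lesions persist for a long time.

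An abstractor who follows section 4 tracks an outpatient to healing but may close an inpatient's case at discharge. Length of follow-up then depends on severity, which section 3 hypothesises to be worse with HIV. In the Kaplan-Meier and Cox analyses of section 7.4 such a patient is censored because of being ill enough to be admitted, which is informative censoring. Another abstractor could enter the discharge date as the resolution date, which turns the sickest patients into early healers. Up to 12 sites in up to 7 countries could settle this differently.

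Other outcomes are touched as well. A readmission, or a complication or death after discharge, would fall outside the record, although section 3.4 needs every stay and section 3.3 lists complications and death as primary.

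**Working it through.** **The passages side by side.** The plan gives no figure on this point, so the check starts with the text. Summing all stays (3.4) needs data after a first discharge. Waiting 90 days (6.2) serves follow-up to that day. Censoring only for lesions unhealed at the end of the study period (7.4) implies that discharge does not censor. Closing a case at discharge defeats all three, yet section 4 permits it.

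**How many patients.** Section 6.1 reports 53 hospitalisations among 907 PLWHIV: 53/907 = 5.8%. Section 1 reports 13% in an early series. Applied to the planned total of about 2000, 0.0584 × 2000 = 117 and 0.13 × 2000 = 260. Neither rate fits exactly. The first covers PLWHIV only. The second is a mixed series (41% with HIV) that includes infection-control admissions, which the footnote to sections 3.3 and 3.4 excludes.

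**Effect on the hazard ratio (illustrative).** The simulation used 1000 PLWHIV, 1000 PrEP users and 300 replicates per scenario.

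- Assumed: Weibull healing time with shape 2 and median 21 days (inside the 2 to 4 weeks), so scale = 21/(ln 2)^(1/2) = 25.2 days.
- Assumed: inpatient median multiplied by 1.0, 1.5 or 2.0.
- Assumed: discharge day = uniform(3, 10) + gamma with mean 7, so the mean is 6.5 + 7 = 13.5 days.
- Admission shares: 5.8% and 13% appear in the documents, but giving 13% to PLWHIV and 5.8% to PrEP users is an assumption. The 20% is wholly assumed.

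HR is PLWHIV against PrEP users; below 1 means slower healing in PLWHIV.

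| Inpatient healing time | Admitted, PLWHIV v PrEP | Followed to healing or day 90 | Censored at discharge | Discharge recorded as healing |
|---|---|---|---|---|
| 1.5× | 13% v 13% | 1.00 | 1.00 | 1.00 |
| 2.0× | 13% v 13% | 1.00 | 1.00 | 1.00 |
| 1.0× | 13% v 5.8% | 1.00 | 1.00 | 1.06 |
| 1.0× | 20% v 5.8% | 1.00 | 1.00 | 1.12 |
| 1.5× | 13% v 5.8% | 0.94 | 0.99 | 1.06 |
| 1.5× | 20% v 5.8% | 0.88 | 0.97 | 1.11 |
| 2.0× | 13% v 5.8% | 0.89 | 0.98 | 1.06 |
| 2.0× | 20% v 5.8% | 0.81 | 0.96 | 1.11 |

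Across all scenarios, 74% to 92% of inpatients were discharged before healing. In the last four rows, censoring at discharge shortened the PLWHIV median by 0.6 (21.94 − 21.38) to 1.5 days (23.39 − 21.90), so the hazard ratio is distorted more than the median.

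**Sensitivity to the assumptions.** With Weibull shape 2.5, medians of 21 and 35 days, discharge at a mean of 10 days and 13% v 5.8% admitted, the HR goes from 0.89 to 1.00 when discharge censors. In the same model with the documents' 5.8% given to PLWHIV and an assumed 3% to PrEP users, it goes from 0.96 to 1.00.

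**The case against.** The strongest reply is that a reader might infer from section 4 that data collection definitely stops at discharge, and the documents do not establish that. The wording is a list of examples, and sections 3.4, 6.2, 7.4 and 7.5 all fit follow-up that continues past discharge. This stands: stopping at discharge is a natural reading but not the only one. It does not remove the problem, because the synopsis and section 4 are the only places that tell a site when to close a case.

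A reader might also infer that the sickest patients are lost from the analysis. They are not: under the censoring reading they contribute time at risk up to discharge.

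Nor do the documents show that the HIV effect will be hidden. Under censoring, the bias needs both unequal admission and slower inpatient healing, and neither is reported. The only admission rate specific to PLWHIV is the 5.8%. If discharge is recorded as healing, the bias runs past 1 instead of towards it, so the reported HR depends on which practice sites adopt.

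Finally, time to lesion resolution is secondary and conditional on being known (3.4), peak lesion severity and having been admitted are largely settled by discharge, and deaths after discharge should be few (1 death among 907 in section 6.1). These points lower the severity. Against them, section 7.4 analyses time to lesion resolution with the primary outcomes.

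**Conclusion.** The concern holds as a conflict in the end-of-data rule. The rule places discharge beside healing and death, gives no precedence, and works against the sections that need data after discharge. About 6% to 13% of patients, roughly 117 to 260 of 2000, could be affected directly.

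If discharge censors, PLWHIV are admitted more often and inpatients heal more slowly, a true HR of about 0.81 to 0.94 would be reported as about 0.96 to 0.99 under the main set of assumptions. If discharge is recorded as healing, the HR would be about 1.06 to 1.12, and unequal admission alone is enough. With equal admission there is no material bias under either practice; with equal healing there is none under censoring. The sizes rest on assumed healing times, discharge times and group admission rates, so they show direction and plausible scale only.

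This is a should-fix. A must-fix rating would need evidence that sites will stop at discharge and that both conditions hold, and the documents supply neither.

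**What to change.** 1. In the synopsis and section 4, remove hospital discharge as an end of data collection.
2. Abstract every case from the existing record to 90 days after diagnosis or death, including lesion resolution, readmissions, complications and deaths after discharge. Let discharge close only each hospital stay.
3. In section 7.4, state that discharge is not a lesion-resolution event and does not in itself end follow-up. Censor unhealed patients at their last documented lesion assessment, at most day 90. Carrying everyone without a healing date to day 90 as unhealed would create the opposite error.
4. Put the same rule in the eCRF guidance, and report by group how many admitted patients have their last lesion assessment at discharge.

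The cost is protocol and eCRF wording and slightly longer abstraction. No visits are needed, since section 5.1 already requires more than 90 days since diagnosis. That guarantees elapsed time, not documentation: some routine records will still end at discharge, and censoring for those patients stays potentially informative.

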5 ELIGIBILITY CRITERIA

The study population will consist of adult PLWHIV and PrEP users who have had confirmed MPX and are followed up at the study sites for routine clinical care.

Cases (PLWHIV + PrEP users) will be at least 18 years of age, with confirmed MPX infection by documented, positive result on PCR testing of lesions from 1st May 2022 to 1st December 2023.

5.1 Inclusion Criteria

- Diagnosis of MPX was more than 90 days prior to data collection
- Confirmed MPX infection by documented PCR testing on skin and/or mucosal and/or any anatomical site between 1st May 2022 to 1st December 2023
- At least 18 years of age
- Cases (PLWHIV + MPX)
 - Documented HIV-1 infection
- Cases (PrEP users + MPX)
 - Attended a clinic to receive PrEP or self-procured PrEP at time of Mpox diagnosis.

5.2 Exclusion Criteria

- MPX diagnosed based on clinical criteria only
- MPX diagnosis was within the last 90 days

6 STUDY PROCEDURES

6.1 Participant Identification

Most People living with HIV (PLWHIV) and HIV negative PrEP users will be identified from sites in the NEAT ID network. PLWHIV are routinely followed-up at specialised outpatient clinics with regular follow up visits as standard of care and many of these centres take care of patients on PrEP. Patients are taking PrEP to prevent contraction of HIV as they perceive themselves to be at risk due to frequent sexual activity with different partners.

In July 2022, NEAT ID opened a dashboard to 150 sites from 20 countries to provide basic information about the number of PLWHIV with MPX and disease outcomes at their centres (<https://www.NEAT-ID.org/>). Data were provided from patients' cases from April 2022 until November 2022 from 31 global sites, 26 sites from 16 European countries and 5 site in Latin America. The dashboard provided a first estimate about the total numbers of PLWHIV with MPX and where these patients are in continued care. As of the end of November 2022, 907 PLWHIV with MPX were reported in care, with 53 hospitalisations and 1 death from an estimated number of 85,279 PLWHIV in routine care at these sites ([name] *et al*, EACS 2023). These case numbers strongly suggested feasibility to recruit sufficient numbers of PLWHIV with MPX and that patients have been identified at their centres already.

A feasibility study of patients receiving PrEP across the NEAT ID network have identified 45 sites that provide PrEP services for a total of 27,416 PrEP users with 1,361 new PrEP initiators each month.

6.2 Data collection

Only real-world retrospective data will be used for this study. Patients who have had mpox and fulfil the entry criteria will be enrolled after 90 days from date of diagnosis to allow for follow up data to be collected. Pseudonymised retrospective data will be transcribed into the eCRF system from source data at each clinical site or from existing cohort databases, where appropriate. No personal identifiable data will be transmitted to NEAT ID. The data elements will be transcribed from source data according to the data collection list below. Mechanisms to ensure data quality and integrity will be deployed as per applicable standard operating procedures and in line with Good Documentation Practice (GDocP) and Good Pharmacoepidemiology Practice (GPP). Patients will be identified and documented by participating sites.

For all patients with MPX the following information will be collected where routinely available:

- Age (year of birth)
- Sex and gender identity
- Ethnicity (where available)
- HIV status
- HIV pre-exposure prophylaxis (PrEP) use
- Comorbidities and Medical history (diabetes mellitus, other immunosuppression (e.g. solid organ transplant), known chronic kidney or liver disease, mental health conditions)
- Recent sexual history (3 months) – number of recent partners
- Recent and/or concomitant sexually transmitted infections
- Orthopoxvirus vaccination history (if available)
- Symptom onset date (fever onset, lesion onset, rectal pain)

- Date of positive PCR test result (documented)
- MPX severity -Reported clinical signs and symptoms of mpox (e.g. rash, mouth lesions, rectal pain, breathlessness)
- Time to resolution of lesions, if known
- Mortality as a consequence of MPX including cause
- Hospitalisation for MPX and length of hospitalisation
- Drug treatment for MPX (Tecovirimat, other)
- Drug for complications associated with MPX (laxatives, antibiotics, analgesia)
- recent travel to/living in endemic country or country with outbreak
- contact with suspected, probable, or confirmed case (if known)
- contact with infected animal (if known)

For PLWHIV the following additional information will be collected:

- Date of HIV diagnosis
- Current Antiretroviral Therapy/Treatment (ART)
- If not on ART, reason for not being on ART
- Last CD4 cell count (including CD4% and CD4/CD8 ratio) and
- Last HIV-RNA before MPX diagnosis

Skin lesion at peak severity score:

- Not presenting with skin lesions (0 skin lesions)
- Mild (<25 lesions)
- Moderate (25-99 skin lesions)
- Severe (100-250 skin lesions)
- Very severe (>250 skin lesions)

Site of lesion will also be collected as part of the severity assessment:

- Genital lesions (defined as involvement of either vulva or vaginal mucosa or penis, pubic area)
- Ano-rectal/perianal lesions
- Oral mucosa (lips/gums/oral/pharynx) lesions
- Face
- Trunk (chest/torso/abdomen/back)
- Limbs (arms/forearms/legs/hands/feet)

Complications which will be collected are as follows:

- Severe rectal and/or perianal pain (i.e. due to perianal/anal abscess, proctitis)
- Tonsillitis and/or dysphagia
- Secondary bacterial infection on affected skin
- Urological complications (genital oedema, urinary retention)
- Ocular involvement (conjunctivitis, corneal involvement, periorbital cellulitis)
- Central nervous system involvement (encephalitis, meningitis, focal neurology signs)
- Pneumonia/pulmonary abscess or necrotizing involvement
- Myocarditis
- Diarrhoea

The definition of a mental health condition will be that reported by the patient and recognized in the ICD-10 classification.

In the UK, severe disease is defined as:

- Adults with severe clinical illness (e.g. National Early Warning Score [NEWS] 2 score of ≥ 5), which may include significant lower respiratory symptoms, confusion/encephalitis, and other complications (e.g. secondary bacterial infection, sepsis)
- Widely disseminated lesions and very many in number (≥ 100)
- Suspected infection of the cornea
- Severe, refractory pain from lesions requiring hospitalisation to achieve symptomatic control
- Lesions associated with complications due to pain or swelling (e.g., constipation, urinary retention, inability to swallow)
- Confirmed infection, regardless of severity, in immunocompromised people, pregnant women, or children aged ≤ 16 years.

7 STATISTICS AND DATA ANALYSIS

7.1 Planned recruitment rate

We believe that approximately 12 sites from 7 countries globally could participate. Therefore, we estimate that an average of 170 patients would need to be recruited per site to reach the total number of subjects required. Recruitment however will be competitive with no upper limit on the number of patients per site.

The patients should be entered into the eCRF in chronological order (i.e. first Mpox patient who was diagnosed with MPX and who meets the criteria entered first etc.)

7.2 Statistical analysis plan

This is primarily a descriptive retrospective data cohort study but will compare MPX severity between 1) PLWHIV and PrEP users, to show whether HIV infection is associated with more severe MPX; 2) PLWHIV with different characteristics, to identify factors associated with severe MPX within HIV infected population.

All enrolled participants who meet the eligibility criteria will be included in the analysis population (full analysis population). All primary and secondary endpoints will be performed with the full analysis population.

